#### 2.9.2 Infusion-related reactions

Infusion-related reactions including hypotension, dyspnea, chills, dizziness, paresthesia, and hypoesthesia were reported during IV administration of isavuconazonium sulfate. The infusion should be discontinued if these reactions occur.

#### 2.9.3 Hypersensitivity reactions

Serious hypersensitivity and severe skin reactions, such as anaphylaxis or Stevens Johnson syndrome, have been reported during treatment with other azole antifungal agents. Isavuconazonium sulfate should be discontinued if a patient develops a severe cutaneous adverse reaction. There is no information regarding cross-sensitivity between isavuconazonium sulfate and other azole antifungal agents. Caution should be used when prescribing isavuconazonium sulfate to patients with hypersensitivity to other azoles.

# 2.9.4 Embryo-fetal toxicity

Isavuconazonium sulfate may cause fetal harm when administered to a pregnant woman and should be used during pregnancy only if the potential benefit to the patient outweighs the risk to the fetus. Perinatal mortality was significantly increased in the offspring of pregnant rats dosed orally with isavuconazonium sulfate at 90 mg/kg/day (less than half the maintenance human dose based on area under the curve (AUC) comparisons) during pregnancy through the weaning period.

Isavuconazonium chloride administration was associated with dose-related increases in the incidences of rudimentary cervical ribs in rats and rabbits at 30 and 45 mg/kg, respectively, doses equivalent to about one fifth and one tenth of the clinical exposures based on AUC comparisons. In rats, dose-related increases in the incidences of zygomatic arch fusion and supernumerary ribs/rudimentary supernumerary ribs were also noted at 30 mg/kg and above, equivalent to one fifth the clinical dose based on AUC comparisons.

#### 2.9.5 Drug particulates

Following dilution, isavuconazonium sulfate IV formulation may form precipitate from the insoluble isavuconazole. The drug, should, therefore, be administered through an in-line filter.

2.10 Adverse events

# Selected Treatment-Emergent Adverse Reactions with Rates of 5% or Greater in Isavuconazonium Sulfate-treated Patients in the SECURE Trial

System Organ Class		
Preferred Term	Tri	al 1
	CRESEMBA	Voriconazole
	(N=257)	(N=259)
	n (%)	n (%)
Gastrointestinal disorders		
Nausea	71 (27.6)	78 (30.1)
Vomiting	64 (24.9)	73 (28.2)
Diarrhea	61 (23.7)	60 (23.2)
Abdominal pain	43 (16.7)	59 (22.8)
Constipation	36 (14.0)	54 (20.8)
Dyspepsia	16 (6.2)	14 (5.4)
General disorders and administration site conditions		
Edema peripheral	39 (15.2)	46 (17.8)
Fatigue	27 (10.5)	18 (6.9)
Chest pain	23 (8.9)	16 (6.2)
Injection site reaction	16 (6.2)	4 (1.5)
Hepatobiliary disorders		
Elevated liver laboratory tests a	44 (17.1)	63 (24.3)
Metabolism and nutrition disorders		
Hypokalemia	49 (19.1)	58 (22.4)
Decreased appetite	22 (8.6)	28 (10.8)
Hypomagnesemia	14 (5.4)	27 (10.4)
Musculoskeletal and connective tissue disorders		
Back pain	26(10.1)	19 (7.3)
Nervous system disorders		

Headache	43 (16.7)	
Psychiatric disorders		
Insomnia	27 (10.5)	25 (9.7)
Delirium b	22 (8.6)	30 (11.6)
Anxiety	21 (8.2)	18 (6.9)
Renal and urinary disorders		
Renal failure	26 (10.1)	21 (8.1)
Respiratory, thoracic and mediastinal disorders		
Dyspnea	44 (17.1)	35 (13.5)
Acute respiratory failure	19 (7.4)	22 (8.5)
Skin and subcutaneous tissue disorders		
Rash	22 (8.6)	36 (13.9)
Pruritus	21 (8.2)	15 (5.8)
Vascular disorders		
Hypotension	21 (8 2)	28 (10.8)

 Elevated liver laboratory tests include reactions of increased alanine aminotransferase, aspartate aminotransferase, blood alkaline phosphatase, blood bilirubin, and gamma-glutamyltransferase.

b Delirium includes adverse reactions of agitation, confusional state, delirium, disorientation, and mental status changes.

The following adverse reactions occurred in less than 5% of all CRESEMBA-treated patients in Trial 1 or 2. The list does not include reactions presented in Table 2. This listing includes adverse reactions where a causal relationship to isavuconazole cannot be ruled out or those which may help the physician in managing the risks to the patients.

#### Blood and lymphatic system disorders: agranulocytosis, leukopenia, pancytopenia

**Cardiac disorders:** atrial fibrillation, atrial flutter, bradycardia, reduced QT interval on electrocardiogram, palpitations, supraventricular extrasystoles, supraventricular tachycardia, ventricular extrasystoles, cardiac arrest

Ear and labyrinth disorders: tinnitus, vertigo

Eye disorders: optic neuropathy

Gastrointestinal disorders: abdominal distension, gastritis, gingivitis, stomatitis

General disorders and administration site conditions: catheter thrombosis, malaise,

chills

Hepatobiliary disorders: cholecystitis, cholelithiasis, hepatitis, hepatomegaly, hepatic

failure

Immune system disorders: hypersensitivity

Injury, poisoning and procedural complications: fall

Metabolism and nutrition disorders: hypoalbuminemia, hypoglycemia, hyponatremia

Musculoskeletal and connective tissue disorders: myositis, bone pain, neck pain

**Nervous system disorders:** convulsion, dysgeusia, encephalopathy, hypoesthesia, migraine, peripheral neuropathy, paraesthesia, somnolence, stupor, syncope, tremor

Psychiatric disorders: confusion, hallucination, depression

Renal and urinary disorders: hematuria, proteinuria

# Respiratory, thoracic and mediastinal disorders: bronchospasm, tachypnea

Skin and subcutaneous tissue disorders: alopecia, dermatitis, exfoliative dermatitis, erythema, petechiae, urticaria

Vascular disorders: thrombophlebitis

# Laboratory effects

In the SECURE trial, elevated liver transaminases (alanine aminotransferase (ALT) or aspartate aminotransferase (AST)) >3 x the upper limit of normal (ULN) were reported at the end of study treatment in 4.4% of patients who received isavuconazonium sulfate. Elevations of liver transaminases >10 x ULN developed in 1.2% of patients who received isavuconazonium sulfate.

# 3. STUDY DESIGN

This is a single-arm, open-label, non-randomized, primary prophylaxis study with a target accrual of 100 patients.

# **4 OBJECTIVES AND ENDPOINTS**

# **4.1 OBJECTIVES**

# 4.1.1 Primary

4.1.1.1 To assess whether prophylaxis with isavuconazole effectively prevents the occurrence of proven or probable IFIs in patients with newly diagnosed AML/MDS receiving successive cycles of intensive chemotherapy or other therapies for up to 100 days from prophylaxis initiation.

# 4.1.2 Secondary

- 4.1.2.1 To evaluate the incidence of IA within 100 days of beginning isavuconazole prophylaxis in newly diagnosed patients with AML/MDS receiving intensive chemotherapy or other therapies.
- 4.1.2.2 To evaluate the incidence of other IFIs within 100 days of beginning isavuconazole prophylaxis in newly diagnosed patients with AML/MDS receiving intensive chemotherapy or other therapies.
- 4.1.2.3 To evaluate the composite outcome of treatment success vs. failure in this patient population (Definition of treatment failure: occurrence of proven or probable IFI, receipt of any other systemic antifungal agent for ≥4 days for suspected IFI, occurrence of an AE possibly or probably related to the study drug resulting in discontinuation of treatment, or withdrawal from the study with no additional follow-up).
- 4.1.2.4 To measure the overall survival (OS) of study participants.
- 4.1.2.5 To measure the IFI-free survival of study participants.
- 4.1.2.6 To document the time to death from any cause in the study population.
- 4.1.2.7 To document the time to death related to IFI in the study population.
- 4.1.2.8 To document the time to diagnosis of proven or probable IFI in the study population.
- 4.1.2.9 To document the time to initiation of empiric anti-fungal therapy in the study population.
- 4.1.2.10 To characterize the safety, tolerability and AE profile of isavuconazole in the prophylactic setting.

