Isavuconazole has several attractive attributes that represent advantages over both voriconazole and posaconazole. The IV formulation is water-soluble, thus eliminating the need for a cyclodextrin vehicle and any resultant nephrotoxicity; it does not cause visual disturbances, hallucinations and photosensitivity, which are common adverse effects (AEs) of voriconazole; it is only a weak inhibitor of P-glycoprotein (P-gp), unlike posaconazole, a strong inhibitor contraindicated, for example, with IDH inhibitors, a class of drugs with great promise in AML; it shortens, rather than prolongs, the QTc

interval, thereby potentially making it safer to use than other azoles with a broad range of tyrosine kinase inhibitors and other medications frequently used in patients with AML (e.g., levofloxacin, ondansetron) that prolong the QTc interval. Indeed, for a variety of reasons mostly related to DDIs, patients with AML are not able to receive optimal prophylactic therapy with broad spectrum anti-mold triazoles (i.e., voriconazole or posaconazole) and are placed on suboptimal prophylactic regimens, e.g., with echinocandins.

Given the broad spectrum of anti-fungal activity, excellent safety and oral bioavailability of isavuconazole, the availability of an IV preparation without nephrotoxic excipients, its improved DDI profile compared to voriconazole and posaconazole, and the shortening, rather than lengthening, of the QTc interval seen with this agent, investigation of its utility in the prophylactic setting in neutropenic patients with AML and other hematologic malignancies and in HCT recipients appears warranted.

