# 4.2.2 Secondary

- 4.2.2.1 Incidence of IA within 100 days of isavuconazole prophylaxis initiation.
- 4.2.2.2 Incidence of other IFIs within 100 days of isavuconazole prophylaxis initiation.
- 4.2.2.3 Rates of treatment success vs. failure (defined above).
- 4.2.2.4 Overall survival.
- 4.2.2.5 Survival without proven or probable IFI.
- 4.2.2.6 Time to death from any cause.
- 4.2.2.7 Time to death related to IFI.
- 4.2.2.8 Time to diagnosis of proven or probable IFI.
- 4.2.2.9 Time to first use of empiric antifungal therapy.
- 4.2.2.10 AEs throughout the duration of isavuconazole prophylaxis until 30 days after the last dose of study drug.

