# 6.2 Duration of prophylaxis

Study drug treatment will be administered daily continuously until, whichever occurs first:

- recovery from neutropenia (ANC  $\geq 0.5 \times 10^9/L$ ) and attainment of complete remission (CR), with or without complete count recovery or
- occurrence of a proven or probable IFI as defined by EORTC/MSG criteria, or
- 12 weeks have elapsed from the start of therapy, or
- development of unacceptable toxicity, or
- patient's withdrawal from the study (patient or investigator decision), or

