#### **Concomitant medications**

- a) All patients may also receive standard antibacterial and antiviral prophylaxis.
- b) No concomitant antifungal therapy is allowed while patients are receiving study drug.
- c) Co-administration of strong CYP3A4 inducers or inhibitors is contraindicated.
- d) Concomitant medications will be entered in the medical record, not the case report form.

	Pre- Study*	Wk 1	Wk 2	Wk 3	Wk 4	Wk 5	Wk 6	Wk 7	Wk 8	Wk 9	Wk 10	Wk 11	Wk 12	Off Study f
Isavuconazonium sulfate		А	А	А	А	А	А	А	А	А	А	А	А	
Informed consent	Х													
Demographics	Х													
Medical history c	Х	х			Х			х			Х			
Concurrent meds	Х	X											X	
Physical exam c	Х	Х			Х			х			Х			Х

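### The success/failure composite in 4.1.2.3 scores a patient moved to another prophylactic antifungal, for a reason other than a related adverse event, as a treatment success

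*Combined protocol and SAP*

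**What the plan says.** Section 4.1.2.3 lists four ways to be a treatment failure:

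1. "occurrence of proven or probable IFI";
2. "receipt of any other systemic antifungal agent for ≥4 days for suspected IFI";
3. "occurrence of an AE possibly or probably related to the study drug resulting in discontinuation of treatment";
4. "withdrawal from the study with no additional follow-up".

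Success has no definition of its own. Endpoint 4.2.2.3 refers back to this list, so success is its complement.

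Section 6.2 ends prophylaxis at neutrophil recovery with complete remission, at 12 weeks, or earlier for IFI, toxicity, death or withdrawal by patient or investigator decision. The concomitant medication list in section 8 bars other antifungals only while study drug is being taken. It also states: "Co-administration of strong CYP3A4 inducers or inhibitors is contraindicated". Section 8.11 keeps patients who stop in toxicity follow-up for 30 days, and section 11 assesses IFI up to day 100 from the start of prophylaxis. The Analysis Plan in section 11 gives binary secondary endpoints a rate with an exact 95% confidence interval. It adds no rule for patients who move to another prophylactic antifungal.

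**The concern.** The composite is the one secondary endpoint that combines infection with tolerance of the drug. A reader will take its success rate as the share of patients whom isavuconazole carried through the risk period. The second component depends on why the other antifungal was given: treatment of a suspected infection counts, replacement prophylaxis does not. A patient could take isavuconazole for a short time, spend the rest of the period on another prophylactic agent, and be reported as a success of isavuconazole.

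Such stops are foreseeable from the protocol: a contraindicated co-medication that becomes necessary after entry, non-adherence, or a decision by the patient or investigator. The misclassification has one direction. Counting these patients otherwise can lower the success rate or leave it unchanged, but cannot raise it.

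**Working it through.** **No figure to reproduce.** The plan states no expected rate, target, margin or power for the composite. The check is therefore a reading of the definition, followed by arithmetic on assumed counts.

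**Step 1. Test the patient against each component.** The patient stops isavuconazole before a planned end of prophylaxis because a contraindicated co-medication is newly needed. The patient then starts another prophylactic antifungal, has no proven or probable IFI, and is followed as sections 8.11 and 11 provide.

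| Failure component (4.1.2.3) | Met? | Reason |
|---|---|---|
| Proven or probable IFI | No | None occurred |
| Other antifungal, 4 days or more, suspected IFI | No | Given as prophylaxis, however long it lasts |
| Related AE that stops treatment | No | The stop was not caused by an AE |
| Withdrawal without further follow-up | No | Follow-up continues |

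No component is met, so the patient is a success. The same holds for non-adherence or a patient or investigator decision, provided follow-up continues.

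**Step 2. Look for a rule elsewhere.** The bar on concomitant antifungals ends when study drug ends. Endpoint 4.2.2.9 concerns empiric antifungal therapy, which on its wording is not replacement prophylaxis. The Analysis Plan is silent. Nothing reclassifies the patient.

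**Step 3. Size.** Inputs: N = 100 (sections 3 and 11). F = failures under the four components and k = replacement switches among the successes; the documents give neither, so both are assumed.

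- Rate as written: (N − F)/N.
- Rate with switches counted as failures: (N − F − k)/N.
- Difference: k/N, which is 1/100 = 1 percentage point per patient.
- Exact (Clopper-Pearson) 95% limits for x successes: lower = 2.5% quantile of Beta(x, N − x + 1); upper = 97.5% quantile of Beta(x + 1, N − x).

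| F (assumed) | As written | k (assumed) | Switches counted as failures |
|---|---|---|---|
| 10 | 90% (82.4–95.1) | 5 | 85% (76.5–91.4) |
| 10 | 90% (82.4–95.1) | 15 | 75% (65.3–83.1) |
| 25 | 75% (65.3–83.1) | 5 | 70% (60.0–78.8) |
| 25 | 75% (65.3–83.1) | 10 | 65% (54.8–74.3) |
| 25 | 75% (65.3–83.1) | 20 | 55% (44.7–65.0) |

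The rate as written does not depend on k. A report of 75% would look the same with no switches as with 20.

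**The case against.** The strongest reply is that the composite is a defensible choice. It defines failure as infection, suspected infection, related intolerance or loss to follow-up. The trial already counts outcomes after study drug ends: IFI is assessed to day 100, while prophylaxis stops at 12 weeks at the latest. On that view, staying on the drug is a different question. This stands as a reason to keep the present version. It is not a reason to leave replacement prophylaxis invisible.

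The routes are also narrower than they first appear. Sections 5.2.5 and 5.2.10 exclude patients who cannot come off strong CYP3A4 inducers or inhibitors, or who need prohibited drugs. Section 6.1 allows a change to the IV form, and sections 5.1.6 and 5.2.9 keep out patients who cannot take or absorb oral medication. Drug-related vomiting that stops treatment is already a failure under the third component. An interaction is not a listed reason for stopping in 6.2 or section 10, so it would act through patient or investigator withdrawal, which is a failure if follow-up also ends. All of this limits the likely number of cases. It does not cover a need that arises after entry in a patient who is still followed.

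A reader might go further and infer that the composite misses the very failure that isavuconazole was chosen to avoid. Section 1.4 does not support that. It says "for a variety of reasons mostly related to DDIs, patients with AML are not able to receive optimal prophylactic therapy", referring to voriconazole and posaconazole. That concerns who can be given those drugs. It does not say that interactions force patients off them, and it is one of several advantages listed. No objective sets out to measure interaction-driven switching.

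**Conclusion.** The gap is real on the text: the four components and their complement classify these patients as successes, and no other section changes that. The size is 1 percentage point per such patient at n=100, always in favour of success. The total is unknown. The counts in the table above are illustrations, and a reader should not infer from them that the reported rate would be wrong by 5 to 20 points. The result assumes that the patient remains in follow-up, as sections 8.11 and 11 plan, and that the stop was not due to a related AE.

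The consequence is limited. This is one of ten secondary endpoints, reported descriptively. A reader might infer that the primary analysis or the monitoring is affected. Neither is: the primary endpoint is proven or probable IFI, and the futility and toxicity rules in section 11 use IFI and toxicity counts. The point is a cheap improvement to the definition and reporting of one endpoint.

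**What to change.** Keep the four-component composite as it is. Prespecify beside it a second version that also counts as failure the start of another systemic antifungal as replacement prophylaxis before a planned end of prophylaxis, meaning neutrophil recovery with complete remission, or 12 weeks. Report both rates with exact 95% intervals. Tabulate the reason for each early discontinuation, with drug interaction on its own line. That table also shows patients who stop without a replacement, who remain successes in both versions if no other component applies.

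Do not widen the new component to discontinuation for any reason. Stopping because of death would then count as failure. Section 1.1 cites 30-day mortality of 5–10% in younger adults and 11–12% in an older population, and 60-day mortality of 21% in secondary AML, so deaths could outnumber switches. Report death without IFI as its own category.

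The costs are two. The second rate can only equal the first or be lower. The reason for stopping, and any replacement antifungal with its start date, must be added to the case report form or taken from charts, because item d of the concomitant medication list puts these drugs in the medical record only. The AE items that section 12 sends to the case report form would not pick up a stop without an AE. Enrolment, treatment, the primary analysis and the stopping rules do not change.

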#### • patient's death

Isavuconazonium sulfate will be provided at no cost to the patients participating in this study.

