# **10 CRITERIA FOR REMOVAL FROM THE STUDY**

Patients will be removed from the study if:

- 12 weeks have elapsed from the start of therapy, or
- The ANC has recovered to ≥0.5 x 10^9/l and CR with or without complete count recovery has been documented (per ELN criteria), or
- A proven or probable IFI has occurred (as defined by the EORTC/MSG), or
- Unacceptable drug toxicity develops, or
- The patient or investigator decide to withdraw the patient from the study, or
- Patient dies while on study.

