Toxicity will be monitored in all patients. Denote the probability of toxicity by p (Tox), where toxicity is defined as any Grade  $\geq$ 3 clinically relevant non-hematologic toxicity, grade  $\geq$ 4 hematologic toxicity lasting  $\geq$ 6 weeks with a hypocellular bone marrow and <5% blasts or a serious adverse event (SAE) that is definitely, probably or possibly related to the study drug (AEs will be graded according to the Common Terminology Criteria for Adverse Events (CTCAE) version 4.0). We assume a priori for toxicity rate, p (tox) ~ beta (0.6, 1.4). The following toxicity stopping rule will be applied in cohort sizes of 10, starting from the 10th patient: the trial will be stopped if Pr(p(tox)> 0.3 | data) > 0.9. That is, we will stop the trial for new patient enrollment if at any time during the study we determine that there is a more than 90% chance that the toxicity rate is more than 30%. Stopping boundaries corresponding to the toxicity monitoring rule are shown in Table 3 below. The operating characteristics for the monitoring are summarized in Table 4. Again, Multe Lean Desktop (version 2.1) was used to generate the toxicity stopping boundaries and the OC table.

Table 3. Toxicity stopping boundaries in cohort sizes of 10.

Number of patients	No. of patients with toxicity that will lead to the tria being stopped			
10	6-10			
20	9-20			
30	13-30			
40	16-40			
50	20-50			
60	23-60			
70	27-70			
80	30-80			
90	33-90			

Table 4. Operating characteristics for toxicity monitoring in cohort sizes of 10 (max sample size = 100).

True toxicity rate	Prob(stop the trial early)	Average sample size
0.1	0.0002	99.9
0.2	0.02	98.6
0.3	0.26	83.1
0.4	0.86	43.5
0.6	1.0	14.4

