# **12 REPORTING REQUIREMENTS**

These guidelines will be followed for the recording and reporting of adverse events and SAEs.

- 1. Baseline events will be recorded in the medical history section of the case report form (CRF) and will include the terminology event name, grade and start date of the event.
  - a. Baseline events are any medical condition, symptom, or clinically significant lab abnormality present before the informed consent form (ICF) is signed.
    - i. Hematologic laboratory abnormalities will not be recorded as baseline events for patients with acute leukemia, myelodysplastic syndrome, chronic lymphocytic leukemia, or chronic myeloid leukemia in blast phase.
    - ii. If exact start date is unknown, month and year or year may be used as the start date of the baseline event.
- 2. The maximum grade of the adverse event will be captured per course of protocol defined visit date.
- 3. These adverse events will be recorded in the case report form:
  - a. Any grade adverse event that is possibly, probably or definitely related to the study drugs(s).
  - b. All serious adverse events regardless of attribution to the study drug(s).
  - c. Any grade adverse event regardless of attribution to the study drug(s) that results in any dose modification.
- 4. Hematologic adverse events will not be recorded or reported for studies in patients with acute leukemia, myelodysplastic syndrome, chronic lymphocytic leukemia, or chronic myeloid leukemia in blast phase except for:
  - a. Prolonged myelosuppression as defined by the NCI-CTCAE criteria specific for leukemia, e.g., marrow hypocellularity on day 42 or later (≥6 weeks) from start of therapy without evidence of leukemia (<5% blasts), or that results in dose modifications, interruptions or meets the protocol definition of DLT or SAE.
- 5. SAEs will be reported according to institutional policy.
- 6. Protocol specific language regarding the recording and reporting of adverse and serious adverse events will be followed in the event of discordance between the protocol and Leukemia Department-specific adverse event recording and reporting guidelines.

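### The treatment-failure composite omits discontinuation for definitely related AEs, does not include death, and has no stated time window

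*Combined protocol and SAP*

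**What the plan says.** Section 4.1.2.3 defines failure only; success is not defined. The four components are proven or probable IFI; at least 4 days of another systemic antifungal for suspected IFI; and then an "AE possibly or probably related to the study drug resulting in discontinuation of treatment, or withdrawal from the study with no additional follow-up". Endpoint 4.2.2.3 adds nothing to this: "Rates of treatment success vs. failure (defined above". The Analysis Plan in Section 11 gives binary secondary endpoints a proportion with an exact 95% confidence interval, and has no rule for deaths.

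Elsewhere the causality scale has three related levels. The toxicity definition in Section 11 includes "or a serious adverse event (SAE) that is definitely, probably or possibly related to the study drug". Section 12 requires the case report form to hold "Any grade adverse event that is possibly, probably or definitely related to the study drugs(s".

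Death and withdrawal are separate items wherever both are listed. Section 6.2 has "patient's withdrawal from the study (patient or investigator decision), or" and then, as its own bullet, "patient's death". Section 10 has "The patient or investigator decide to withdraw the patient from the study, or" and, again separately, "Patient dies while on study".

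Endpoints 4.2.2.1 and 4.2.2.2 each carry a 100-day limit. Endpoint 4.2.2.3, the next in the list, carries none.

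**The concern.** The AE component leaves out the most certain level of drug causality: stopping for a possibly related AE is a failure, but stopping for a definitely related one is not. This is probably a drafting slip, but it is the only definition in the plan.

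The death gap is less obvious. The composite penalises loss of follow-up but not death, so a success rate read alone could include patients who died early. Because neither success nor the window is defined, two analysts could report different rates from the same data and both claim to have followed the protocol. The trial has a single arm, so no control group would share the same definition and expose its effect.

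**Working it through.** The documents give no expected rate, sample size or power for this composite, so there is no figure to reproduce. The check is to apply the definition literally.

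**Step 1. Classify five hypothetical patients.** Success is taken as the complement of failure (an assumption, since the plan does not say so). Each patient has only the feature shown.

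| Patient | Component met | Literal result |
|---|---|---|
| A. Stops for an AE rated possibly related | AE component | Failure |
| B. Stops for an AE rated definitely related | None | Success |
| C. Dies early; no IFI, no other antifungal, no related AE | None | Success |
| D. Dies early with possible IFI and under 4 days of another antifungal | None | Success |
| E. Withdraws with no further follow-up | Withdrawal component | Failure |

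B against A shows the causality gap. C against E shows the death gap. D shows that the gap is not limited to deaths without fungal disease: the IFI component needs a proven or probable diagnosis, and Section 9.2 makes possible IFI a separate category. A death from a possibly or probably related AE arguably meets the AE component.

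**Step 2. Can death be read as withdrawal?** Sections 6.2 and 10 describe withdrawal as a decision by the patient or investigator and list death as a different item. The withdrawal component therefore does not cover death.

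**Step 3. Size per case.** With n = 100 (Section 11), reclassifying k patients changes the rate by k/100, which is k percentage points.

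Illustration only, with all counts assumed. The exact limits are the 0.025 quantile of Beta(x, n − x + 1) and the 0.975 quantile of Beta(x + 1, n − x).

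| Literal failures | Reclassified cases | Failure rate (exact 95% CI) |
|---|---|---|
| 20 | 0 | 20% (12.7 to 29.2) |
| 20 | 1 | 21% (13.5 to 30.3) |
| 20 | 5 | 25% (16.9 to 34.7) |
| 20 | 10 | 30% (21.2 to 40.0) |

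From 10 literal failures, 10 reclassified cases give 10% (4.9 to 17.6) to 20% (12.7 to 29.2). From 30, they give 30% (21.2 to 40.0) to 40% (30.3 to 50.3).

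**Step 4. Is day-100 status already collected?** Section 8.11 follows patients for 30 (±5) days after therapy ends. That reaches day 100 if treatment lasts to about day 100 − 30 = 70 (range 100 − 35 = 65 to 100 − 25 = 75). A patient treated for the full 12 weeks is covered to 84 + 30 = day 114 (109 to 119). Patients who stop before about day 65 to 75 may not be covered.

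**The case against.** The strongest reply is that the omission of *definitely* is a slip that any analyst would correct, and that leaving death out is a coherent choice. A prophylaxis composite limited to breakthrough infection, need for other antifungals, drug intolerance and loss to follow-up measures what prophylaxis can influence. Counting leukemia deaths would turn it partly into a measure of AML mortality. Deaths are already reported through overall survival, IFI-free survival and the two time-to-death endpoints (4.2.2.4 to 4.2.2.7).

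Much of this stands. It is a reason not to insist that death be a failure in the main rate. It does not excuse leaving the rule unstated, because the other endpoints do not show how deaths were classified within the success rate. Correcting the slip in practice would still depart from the written definition.

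Some stronger readings are tempting but not supported:

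- **Using the mortality in Section 1.1 to size the effect.** A reader might infer a shift of 5 to 21 points from the quoted 5-10%, 13% and 21%. Those are 30- and 60-day figures from other cohorts, including secondary AML. The documents do not say what share of deaths would already meet another component.
- **Assuming that all IFI-related deaths already fail.** Patient D shows otherwise.
- **Assuming that assessment ends at 12 weeks.** Section 10 removes patients from the study then, but Section 8.11 continues toxicity follow-up and Section 11 continues IFI assessment to day 100.

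**Conclusion.** The causality wording is wrong as written: it conflicts with the scale in Sections 11 and 12 and classifies the clearest drug-related discontinuations as non-failures. The handling of death is a gap in specification. On the complement reading, early deaths with no other component, including some with possible IFI, count as successes. The missing window adds to this, because *early* has no cut-off for the composite.

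The size is 1 percentage point per affected patient at n = 100. The total cannot be estimated: the documents give no rate of definitely related discontinuation and no 100-day mortality for this population. The conclusion rests on a literal reading and on success being the complement of failure.

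The consequence is limited to one descriptive secondary endpoint with no test or threshold. A reader might infer that the main result or the safety monitoring is affected. Neither is: the primary endpoint and IFI rule count only proven or probable IFI, and the toxicity rule has its own definition, which already includes *definitely*.

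**What to change.** In Section 4.1.2.3, with a matching sentence in the Analysis Plan:

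1. Word the AE component as possibly, probably or definitely related.
2. Apply the primary endpoint's 100-day window, from the start of prophylaxis, to every component.
3. State that success is the absence of every component within that window.
4. Report the success rate, with its exact 95% confidence interval, twice: with deaths by day 100 that have no other component counted as failures, and with them not so counted. Which is the main rate can be left to the investigators, provided it is stated before analysis.

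The withdrawal component can stay as worded.

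The first change is free, because Section 12 already puts definitely related AEs on the case report form. Antifungal use must be abstracted to day 100 from the medical record, where concomitant medications are kept; endpoint 4.2.2.9 already needs part of this. Day-100 vital status must be checked for patients who stop early. Overall survival needs most of that anyway, but Section 6.5 plans contact only every 6 to 12 months and under a separate consent. The remaining cost is a second reported rate, which will be lower if such deaths occur.
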